- 4) Patients with T Cell ALL must be in complete remission and MRD negative (-) by flow cytometry and molecular studies.
- 5) Patients \geq 18 years of age.
- 6) Karnofsky greater than or equal to 80%.
- 7) CMV seropositive.
- 8) Donor is either matched related, matched unrelated, mismatched unrelated, or haploidentical. Cord blood recipients are also eligible.
- 9) Hgb greater than 10 g/L.
- 10) Patient or patient's legal representative, parent(s) or guardian able to provide written informed consent.
- 11) Negative pregnancy test in female patients of childbearing potential.
- 12) STEP 2: Eligibility at time of generating and infusing CMV-specific cytotoxic T cells (adoptive immunotherapy): CMV reactivation defined as CMV DNAemia \geq 137 copies/ml.
- 13) Evidence of neutrophil engraftment defined as the absolute neutrophil count (ANC) $> 0.5 \times 10^3$ /for 3 consecutive days.
- 14) Clinical status to allow tapering of steroids to less than 0.5 mg/kg/day prednisone or equivalent.
- 15) Negative pregnancy test in female patients of childbearing potential.

Exclusion:

- 1) STEP 1: Within 30 days of study entry: T cell leukemia or lymphoma.
- 2) CMV seronegative.
- 3) Positive for HIV, HBV, HCV, HTLV1 and/or HTLV2.
- 4) STEP 2: Eligibility at time of generating and infusing CMV-specific cytotoxic T cells (adoptive immunotherapy): Documented CMV end-organ disease.
- 5) Patients receiving ATG, or Campath within 28 days of CMV reactivation.
- 6) Patients with other uncontrolled infections. For bacterial infections, patients must be receiving definitive therapy and have no signs of progressing infection for 72 hours prior to generating CTLs. For fungal infections patients must be receiving definitive systemic anti-fungal therapy and have no signs of progressing infection for 1 week prior to generating CTLs. Progressing infection is defined as hemodynamic instability attributable to sepsis or new symptoms, worsening physical signs or radiographic findings attributable to infection. Persisting fever without other signs or symptoms will not be interpreted as progressing infection.

- 7) Patients who have received donor lymphocyte infusion (DLI) within 28 days.
- 8) Patients with active acute GVHD grades II-IV.
- 9) Active and uncontrolled relapse of malignancy.

Are patients <18 years of age eligible to participate in this study? Yes No

Studies that include children must meet the criteria for inclusion.

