http://www.fda.gov/ohrms/dockets/AC/04/briefing/4028B1_05_NIH-Inclusion%20of%20Children.doc
<http://www.hhs.gov/ohrp/policy/populations/children.html>

Studies that exclude children must have appropriate justification. Please select all that apply:

Phase II or III study with no Phase I data for the drug in pediatrics.

Please provide a letter from the Sponsor stating if a Phase I study planned for patients <18 years of age. (May include file attachment)

- This is a rare disease in pediatric patients
- Our Pediatric transplant program is very small
- Our sponsor does not allow pediatric patients to be included in this study.

Are participants >65 years of age eligible to participate in this study? Yes No

Are pregnant women eligible to participate in this study? Yes No

Will the recruitment population at M. D. Anderson include persons who are incarcerated at time of enrollment (e.g., prisoners) or likely to become incarcerated during the study?

Yes No

Disease Group:

Blood And Marrow Transplantation, Leukemia, Lymphoma

Treatment Agents/Devices/Interventions:

CMV-specific CTLs

Proposed Treatment/Study Plan:

Is treatment assignment randomized? Yes No

Is this a blinded or double-blinded study? Yes No

Collection of peripheral blood mononuclear cells (PBMC) for manufacturing of CTLs

After enrollment, PBMC will be collected via venipuncture.

Venipuncture: up to 500 mL one time at the MD Anderson Blood Bank. The product will be cryopreserved for future use to generate CMV-specific CTLs.

PBMCs will be stored for 3 years. If the PBMCs are not needed to generate CTLs, they will be discarded.

Allogeneic HSCT and follow-up

1. Patients will undergo allogeneic HSCT per institutional guidelines.
2. CMV reactivation will be monitored by checking CMV DNA level by polymerase chain reaction (PCR).

Manufacture of recipient derived autologous CMV specific CTLs under GMP conditions

1. After documentation of CMV reactivation, defined as CMV DNA load is equal to or greater than 137 copies/ml, cryopreserved PBMC product of eligible patients' defined under "Eligibility" will be used for generation of CMV-specific CTLs.

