2. Manufacture of recipient derived autologous CMV specific CTLs under GMP conditions will be performed at the MDACC GMP facility. Cryopreserved PBMC product from the recipient will be thawed, washed and diluted at 1×10^9 cells in 100 mL MACS GMP TexMACS Reagent (Miltenyi Biotec) for approximately 16 hours at 37°C (overnight). The product will then be stimulated with MACS® GMP Peptivator® HCMV pp65 (Miltenyi Biotec) for approximately 4 hours at 37°C, CO₂. Once incubation is completed the product will be washed and concentrated with TexMACS Reagent followed by an incubation with CliniMACS IFN-Gamma Catch Matrix Reagent (Cytokine-Secretion-System, Miltenyi Biotec). The stimulated cells will then be washed with CliniMACS buffer to stop stimulation reaction.

After culture, magnetic enrichment of cytokine-secreting cells will be performed with the use of the CliniMACS Enrichment Reagent (Cytokine-Secretion-System) and the CliniMACS device (Miltenyi Biotec). CMV-specific T cells will be infused directly after the isolation procedure without any further in vitro expansion. The purity of the isolated pp65-specific T cells will be assessed by detection of IFN- γ + cells in flow cytometry, with release criteria of $\geq 3\%$ IFN- γ +T cells.

Administration and Monitoring of CTL infusion

1. Premedication for CTL infusion: acetaminophen up to 650 mg (or 10 to 15 mg/kg recipient weight) and diphenhydramine up to 50 mg (or up to 0.5 to 1 mg/kg recipient weight) should be given orally or IV prior to CTL infusion and may be repeated 4 hours later.
2. It is essential to avoid steroid as those may interfere with the efficacy of the infused CMV-specific CTLs. Steroids will be given only if the patient develops a severe or life threatening reaction to the infused CMV-specific CTLs.
3. CTL Administration: The CTL product will be given as single infusion within 72 hours of CMV reactivation.)
4. Patients will be monitored according to institutional standards for administration of blood products and at a minimum will be monitored according to below:
 - Patients should remain in the clinic for at least one hour.
 - Patients should remain on continuous pulse oximetry for at least 30 minutes.
 - Vital signs should be monitored at the end of infusion then at 30 and 60 minutes.
5. CTL dose infused will be at a maximum dose of 10e5 viable CD3+ T cells/kg.

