6. The first three patients on protocol will be observed for at least 28 days for safety monitoring before more patients are enrolled in the study.

Supportive care

1. All patients should receive supportive care as clinically indicated.
2. It is essential to avoid steroid as those may interfere with the efficacy of the infused CMV-specific CTLs.
3. Steroids will be given only if the patient develops a severe or life-threatening reaction to the infused CMV-specific CTLs.

Initiation of anti-viral therapy

1. CMV viral load will be monitored at least weekly by PCR within the 28 days of autologous recipient-derived CMV-specific CTL infusion.

2. Indication to initiate anti-viral therapy will be determined by their response status as described in Table 4.

Table 4. Time-table for monitoring efficacy and initiation of anti-viral drugs

Monitoring	Day 5-7	Day 12-14	Day 19-21	Day 26-28
CMV DNA increase > 50% compared with baseline	X	X	X	X
CMV DNA \geq 5000 copies/ml	X	X	X	X
CMV DNA decrease < 50% compared with baseline			X	
CMV end-organ disease	X	X	X	X
X, indication to start anti-viral therapy				

Management of potential treatment toxicity

1. Microbial contamination of T-cell product.

There is a potential that processing the T-cell product will inadvertently introduce microorganisms that could cause infection in the recipient after the cells are infused. Cultures of the T-cell product will be obtained to monitor for contamination. In the event that a microbial contamination is discovered after infusion of CTLs, standard GMP procedures will be followed.

2. Graft failure: Graft failure is initial neutrophil engraftment followed by subsequent decline in the ANC to $< 500/\text{mm}^3$ for three consecutive measurements on different days, unresponsive to growth factor therapy that persists for at least 14 days in the absence of a known cause such as relapse. GF will be monitored as clinically indicated for the first 6 months after CTL infusion.

3. Graft Versus Host Disease (GVHD)

The risk of GVHD following the infusion of recipient-derived autologous CTLs is expected to be low.

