Statistical Considerations:

Treatment and Primary Outcomes. This is a single-arm phase II trial of autologous virus specific CTLs for CMV reactivation in patients with hematologic malignancies (excluding T cell leukemia and lymphoma) undergoing CMV seronegative matched unrelated donor (MUD), mismatched unrelated or cord blood allogeneic stem cell transplant. Whole blood will be collected and frozen prior to transplant. After documentation of CMV reactivation, defined as CMV at a level ≥ 137 DNA copies/ml by PCR, autologous CMV-specific CTLs will be generated to be infused within 72 hours of CMV reactivation, if the patient has ANC engraftment, no acute GVHD or steroid administration ≤ 0.5 mg/kg dose. All outcomes will be recorded starting from the time of T-cell administration. While the dose of T-cells will vary depending on how many cells can be grown by ex vivo expansion after thawing and prior to administration, the maximum dose will be $10e5$ viable CD3+ T cells/kg. It is anticipated that 20-25 patients per year will be accrued and that approximately 2 patients per month will develop CMV reactivation and thus be eligible to receive autologous CTLs. A maximum of 36 patients will receive autologous CTLs. The two primary endpoints, starting at the time of autologous T-cell administration, will be $T =$ time to non-relapse mortality and $Y =$ [28-day success], where "success" is defined as follows. CMV will be evaluated weekly at 7, 14, 21 and 28 days using PCR. Treatment will be considered a success if the patient does not require initiation of CMV anti-viral therapy. Anti-viral therapy will be started if 1) End-organ disease is documented at any time point after CTL administration 2) Increase in CMV DNAemia $>50\%$ compared with baseline at any time point 3) Decrease in CMV DNAemia $<50\%$ compared with baseline at day 21 after CTL administration and 4) CMV DNAemia >5000 copies/ml at any time point.

Non-relapse mortality is defined as death because of causes other than relapse of the underlying hematological malignancy. Relapse of underlying hematological malignancy will be a competing event for non-relapse mortality. Time to non-relapse mortality is defined as time to non-relapse mortality from date

of stem cell transplantation.

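### Step 2 sets a CMV DNA floor of 137 copies/ml but no ceiling, so a patient already at the plan's own 5000 copies/ml rescue level can be infused

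*Combined protocol and SAP*

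**What the plan says.** **Entry.** Inclusion criterion 12 (Step 2, applied when the cells are generated and infused) requires "CMV reactivation defined as CMV DNAemia \geq 137 copies/ml". The manufacturing section repeats the floor ("defined as CMV DNA load is equal to or greater than 137 copies/ml"), and so does Treatment and Primary Outcomes under Statistical Considerations. None of the three gives an upper limit. The other Step 2 criteria cover engraftment, steroids, pregnancy, ATG or Campath, other infections, donor lymphocytes, acute GVHD and relapse. The one exclusion for CMV severity is "Documented CMV end-organ disease".

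**Infusion.** "The CTL product will be given as single infusion within 72 hours of CMV reactivation". This limits the delay, not the load.

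**After infusion.** "CMV viral load will be monitored at least weekly by PCR within the 28 days" of infusion. Table 4 lists "CMV DNA \geq 5000 copies/ml" as an indication for anti-virals at each of its four windows, the first being day 5-7. Treatment and Primary Outcomes says "CMV will be evaluated weekly at 7, 14, 21 and 28 days using PCR" and gives the trigger as "CMV DNAemia >5000 copies/ml at any time point". It defines 28-day success as not requiring anti-virals, so meeting a trigger is a failure on that primary endpoint.

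**The concern.** Two of the rescue triggers do not depend on the baseline value: end-organ disease and the 5000 level. A patient who already has end-organ disease cannot enter Step 2. A patient already at 5000 can.

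Two things are at stake. The first is care: the plan regards 5000 copies/ml as a load that calls for anti-virals, yet a patient at that load before infusion can be given cells and then wait for the first scheduled check. Earlier PCR is allowed but not required. The second is the endpoint: for such a patient the 28-day result depends partly on the load at entry, and the two descriptions of the trigger need not give the same score. At most 36 patients are treated and the response boundaries start at 0/5, so individual results carry weight.

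**Working it through.** **1. The two readings of the trigger.** Take a patient at 6000 copies/ml on the day of infusion.

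- Treatment and Primary Outcomes: the 5000 trigger applies at any time point. The end-organ item in the same list is limited to the period after CTL administration; the 5000 item carries no such limit. If the infusion-time value counts, anti-virals are due and the patient is a failure at once.
- Table 4: the first window is day 5-7. The patient may go without anti-virals until then, and fails at that check unless the load is below 5000.

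**2. Fall needed by the first check (Table 4 reading).** Required fall = 1 - 5000/baseline, and the actual fall must exceed it.

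| Baseline (copies/ml) | Fall needed by day 5-7 |
|---|---|
| 6000 | 1 - 5000/6000 = 16.7% |
| 10,000 | 1 - 5000/10,000 = 50% |
| 20,000 | 1 - 5000/20,000 = 75% |

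The general rule asks for a 50% fall, and only at day 21. Above 10,000 the 5000 level asks for a larger fall, and asks for it about two weeks sooner. A 70% fall from 20,000 leaves 0.30 × 20,000 = 6000, which is still a failure at day 5-7.

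**3. Can the case arise?** 5000/137 = 36.5, and log2(36.5) = 5.19 doublings.

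- From 137 to 5000 within the 72-hour window: 3/5.19 = 0.58 days per doubling.
- If PCR before infusion is weekly (an assumption; the plan gives no interval), a load just under 137 at one test, found positive 7 days later and infused 3 days after that, reaches 5000 at 10/5.19 = 1.93 days per doubling.

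The documents give no viral growth rate. This shows only that the case is possible.

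**4. The plan's own stopping figures.** An exact binomial recursion over the listed boundaries (0/5 to 10/34, checked after every patient, maximum 36) gives a stopping probability of 0.070 at a success probability of 0.50 and 0.681 at 0.30. Both match Table 7.

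For illustration only, let a share f of infused patients enter at 5000 or more and succeed at 0.25, while the others succeed at 0.50. Neither f nor 0.25 is in the documents.

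- f = 2%: 0.98 × 0.50 + 0.02 × 0.25 = 0.495; stopping probability 0.076.
- f = 5%: 0.95 × 0.50 + 0.05 × 0.25 = 0.4875; stopping probability 0.085.

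If 0.50 describes all infused patients, which is the natural reading of the stopping-rule text, there is no shift.

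**5. Effect of a ceiling on accrual.** The Sample Size paragraph takes the number treatable as binomial with rate 0.40. P(at least 36 of 105) = 0.903, and 105 is the smallest enrolment giving 90%, as the plan states.

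| Otherwise treatable patients excluded (assumed) | Treatable rate | P(at least 36 of 105) | Enrolment for 90% |
|---|---|---|---|
| none | 0.40 | 0.903 | 105 |
| 2% | 0.40 × 0.98 = 0.392 | 0.872 | 108 |
| 5% | 0.40 × 0.95 = 0.38 | 0.811 | 111 |

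**The case against.** **The case is rare by design.** Treatment starts at a very low load and infusion follows within 72 hours. Reaching 5000 from 137 in that window needs very fast growth, and the 10-day route needs an assumed weekly test, a near miss at one test and the full 72 hours. This stands as a limit on size. It does not rule the case out, since the plan states no PCR interval before infusion.

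**Failure is not automatic.** A reader might infer that a patient infused at 5000 is bound to fail. The documents do not support that in general: Table 4 first applies the trigger at day 5-7, and a patient who has fallen below 5000 by then does not meet it. Immediate failure follows only if the infusion-time value counts under the Statistical Considerations wording, and that is unclear.

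**End-organ disease may be excluded for a different reason.** The trial is of pre-emptive therapy, so established disease lies outside the indication. A high load without disease is still reactivation. This stands in part: the parallel does not prove an oversight, and infusing such patients could be a deliberate choice. The plan does not say that it is.

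**The ceiling moves the cliff.** Between 5000/1.5 = 3333 and 5000 the absolute limit still binds before the 50% rise rule: 5000/4000 - 1 = 25% from 4000, and 5000/4900 - 1 = 2% from 4900. This is true. The ceiling does stop infusion of patients who are already at the rescue level.

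**Conclusion.** The point holds as a cheap improvement of low severity. The eligibility text permits infusion at or above the load at which the plan itself calls for anti-virals. Followed as written, that ends badly on either reading: the patient is infused and fails at once, or can be left without anti-virals until day 5-7 and fails unless the load has come below 5000.

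A reader might go on to infer that the operating characteristics are wrong or the efficacy estimate materially biased. The documents do not support this. The response-rule figures in Table 7 reproduce, the frequency of such patients is not given and is probably low, and the shift to 0.076 or 0.085 rests on assumed values. Any added failures would count against the treatment, not for it.

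**What to change.** Add a Step 2 exclusion beside the end-organ one: last CMV DNA before infusion of 5000 copies/ml or more. Treat these patients with standard anti-virals. Step 2 already applies both when the cells are generated and when they are infused, so check the value at both points. The threshold is the sponsor's own, taken from Table 4.

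The cost is one eligibility line by amendment, a slightly narrower population, and a restated enrolment figure in Accrual Comments and Sample Size. If 2% to 5% of otherwise treatable patients were excluded, restoring the 90% assurance takes 3 to 6 more enrolled. At the Sample Size paragraph's 5 per month, that is 3/5 = 0.6 to 6/5 = 1.2 months. Occasionally a product would be made and not infused because the load crossed 5000 in between.

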Sample Size. The effective sample size for evaluating CTL effects is the number of patients who suffer CMV reactivation, are eligible to receive CTLs, and actually receive CTLs, not the number enrolled and undergoing a transplant. In order to obtain a maximum of 36 patients who are treated with CTLs, assuming an accrual rate of 5 patients per month who receive a transplant and a 40% rate of patients with CMV who satisfy the entry criteria for receiving CTLs, it is expected that an effective accrual rate total of 2 patients per month will be enrolled, receive a transplant, and subsequently develop CMV. Due to the randomness of the treatable CMV subsample size, which is binomial in $q = .40$ and $n =$ number of patients initially enrolled and transplanted, up to 105 patients will be enrolled (21 months accrual) to ensure at least a 90% probability that there will be at least 36 patients with CMV. If $q = .50$, then up to 83 patients (17 months accrual) will be enrolled to ensure this same sample size with this reliability. The overall sample size of 36 will ensure that, if the trial is not stopped early and, for example, 18/36 patients achieve 28-day success, then a posterior 95% credible interval for p starting with a beta (.50,.50) prior would be .342 - .658, or approximately 34% to 66%.

The first three patients on protocol will be observed for at least 28 days for safety monitoring before more patients are enrolled in the study.

Statistical Models and Early Stopping Rules

Probability of 28-day Success. The Bayesian method of Thall and Sung will be used to monitor the $p =$ the probability of 28-day success. Assume that the number of 28-day successes $Y \sim \text{binomial}(p, 36)$ and that *a priori* $p \sim \text{beta}(.5, .5)$. The trial will be stopped early if $\text{Pr}(p > .50 \mid \text{data}) < 0.010$. Assuming a $\text{beta}(500, 500)$ prior for the standard response probability, and monitoring continuously, the trial will be stopped early if $[\# \text{ patients with 28-day success}] / [\# \text{ patients evaluated for 28-day success}]$ is less than or equal to $0/5, 1/9, 2/12, 3/15, 4/18, 5/21, 6/24, 7/26, 8/29, 9/31, \text{ or } 10/34$.

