Treatment Failure Event. Treatment failure event is defined as death, graft failure, or grade 3-4 toxicity secondary to CTL infusion in 6 months after CTL infusion. The Bayesian method of Thall, et al. will be used to monitor non-relapse mortality (regimen-related death, RRD). Assume that $T \sim \text{exponential}$ with median m , and that *a priori* $m \sim \text{inverse gamma}(3, 13.9)$, which has mean 6.96, corresponding to historical probability $\text{Pr}(T < 6 \text{ months}) = 0.45$. The trial will be stopped early if $\text{Pr}(m > 6.96 \text{ months} \mid \text{data}) < 0.0717$. In terms of median of T , the early stopping event is $[m > 6.96 \text{ months}]$, which is equivalent to $[\text{mean}(T) > 10.04 \text{ months}]$ because T follows an exponential distribution.

Early Deaths. If a patient treated for CMV dies from any cause before day 28, or drops out for some reason, that will be counted as a failure when scoring 28-day success. Due to the lack of computer software to jointly model the two different types of death, regimen-related and not regimen-related, which are competing risks, and non-fatal 28-day failure, and implement a design which separates these events, if a death within 28-days is regimen-related, then the design will "double count" the event. Specifically, such a death will be scored as an event in the monitoring rule for m and also as a 28-day failure in the monitoring rule for p . Consequently, the monitoring rules are conservative. It is anticipated, however, that the actual probability of such very early deaths will be very small, so these considerations will not substantively affect trial conduct.

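### Time to non-relapse mortality, a co-primary endpoint, is given two different start dates: CTL infusion and stem cell transplantation

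*Combined protocol and SAP*

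**What the plan says.** All references are to the combined protocol and SAP, Statistical Considerations, unless stated.

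- **Infusion as origin.** Treatment and Primary Outcomes states: "All outcomes will be recorded starting from the time of T-cell administration". It then introduces T and Y with: "The two primary endpoints, starting at the time of autologous T-cell administration, will be" T = time to non-relapse mortality and Y = 28-day success.
- **Transplant as origin.** The next paragraph, which defines NRM, first makes relapse a competing event ("Relapse of underlying hematological malignancy will be a competing event for non-relapse mortality"). It ends: "Time to non-relapse mortality is defined as time to non-relapse mortality from date" "of stem cell transplantation". The break inside that sentence is a page break, and the sentence is complete.
- **Who is analysed.** Under Sample Size, the patients who count are those who reactivate CMV, "are eligible to receive CTLs, and actually receive CTLs, not the number enrolled and undergoing a transplant". The Step 2 inclusion criteria (items 12 and 13) require CMV reactivation and neutrophil engraftment before infusion.
- **The monitored event.** Treatment Failure Event covers death, graft failure, or "grade 3-4 toxicity secondary to CTL infusion in 6 months after CTL infusion". It gives a historical probability of 0.45 for T below 6 months and does not say from which date that was counted.
- **The stopping rule.** Stopping Rules reduces the data to the number of events and TFU, the total follow-up time. No start date is given for TFU.

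**The concern.** The two sentences define the same co-primary endpoint on two clocks. For every treated patient they differ by the time from transplant to infusion, which is always positive. The transplant sentence is the one worded as the formal definition, so an analyst who followed it would be doing what the plan says. A second analyst who followed the preceding paragraph would report a different NRM from the same patients.

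The difference has a known direction. A patient who dies between transplant and infusion never receives CTLs and never enters the analysis. On the transplant clock this stretch is immortal time: it adds survival that the selection guarantees and that the product did not produce. The plan does not provide for delayed entry, which would remove it.

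**Working it through.** **1. Direction, with no assumed rate.** Let T be the time from infusion and D > 0 the time from transplant to infusion. On the transplant clock the event time is T + D. For a fixed D (and, by averaging, for a D that varies between patients):

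P(T + D ≤ t, NRM) = P(T ≤ t − D, NRM) ≤ P(T ≤ t, NRM).

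The transplant clock cannot raise NRM at any fixed time t, and it lowers it wherever events can occur between t − D and t. A competing relapse does not change this.

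**2. Size.** The documents give no D (only infusion within 72 hours of reactivation) and no time point at which NRM is to be reported. Assumptions: D = 0.5, 1 or 2 months for all patients, constant hazards, and the 6-month horizon borrowed from Treatment Failure Event.

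Without relapse, if p is the 6-month NRM from infusion, λ = −ln(1 − p)/6, and NRM at 6 months from transplant is 1 − exp(−λ(6 − D)). For p = 0.60, λ = 0.9163/6 = 0.1527. At D = 1 this gives 1 − exp(−0.1527 × 5) = 0.534.

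With relapse at assumed 6-month incidence r, let a and b be the hazards of NRM and relapse. Then a + b = −ln(1 − p − r)/6 and a/(a + b) = p/(p + r). NRM is [a/(a + b)] × [1 − exp(−(a + b)(6 − D))].

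| 6-month NRM from infusion | Relapse | D = 0.5 | D = 1 | D = 2 |
|---|---|---|---|---|
| 0.45 | none | 0.422 | 0.392 | 0.329 |
| 0.60 | none | 0.568 | 0.534 | 0.457 |
| 0.60 | 0.10 | 0.573 | 0.543 | 0.473 |
| 0.60 | 0.20 | 0.578 | 0.554 | 0.494 |
| 0.60 | 0.30 | 0.586 | 0.569 | 0.523 |

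**3. Stopping rule, only if the transplant clock also fed TFU.** The plan's own figures come first. With the prior inverse gamma(3, 13.9), 30-day months and TFU in days,

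Pr(m > 6.96 | data) = GammaCDF((13.9 + TFU/30)/6.96; shape 3 + events).

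The three worked examples give 0.066, 0.089 and 0.062, as printed. Also 1 − 2^(−6/6.96) = 0.450, the historical rate.

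Longer TFU raises this probability and so makes stopping less likely. General point 1 in Stopping Rules says the reverse, but Examples 1 and 2 contradict it: with 3 events each, TFU 170 gives 0.066 and TFU 220 gives 0.089.

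Adding 14 days per patient takes TFU to 226, 276 and 403 days and the examples to 0.092, 0.119 and 0.103. Against the 0.0717 cut-off, Example 1 changes from stop to continue once D exceeds about 3.2 days, and Example 3 at about 3.7 days.

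The printed examples are matched only when TFU is not multiplied by ln 2, although m is called a median. With ln 2 the examples would read 0.046, 0.059 and 0.034, and the changes for Examples 1 and 3 would come at about 23.5 and 24.6 days.

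A simulation used 36 patients, 2 per month, exponential T from infusion, no relapse, and a check at each event up to the last infusion. The ranges are follow-up capped at 6 months or uncapped. At a 6-month risk of 0.60, the stopping probability was 0.37–0.40 at D = 0, 0.17–0.19 at 0.5, 0.06–0.07 at 1 and below 0.01 at 2 months.

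These values are approximate. At D = 0 the simulation gives 0.08–0.09, 0.37–0.40 and 0.56–0.62 at risks 0.45, 0.60 and 0.65. Table 7 states 0.100, 0.374 and 0.648. A different look schedule gave 0.055, 0.346 and 0.536. With the ln 2 update, D = 0 at risk 0.60 gives 0.80–0.875, falling to 0.12–0.20 at 2 months. The direction is the same under every version.

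**The case against.** The strongest reply is that the rest of the plan nearly settles the matter. The sentence that introduces T, the sentence on all outcomes and the 6-month window of the monitored event all point to infusion, as do the worked examples with events at 15 to 50 days. One sentence stands against them, so this could be called a drafting slip. That is fair as to which reading is better. It does not remove the contradiction, because the dissenting sentence is the formal definition of a co-primary endpoint.

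Three further points stand as limits:

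- No sentence says that TFU runs from transplant. The stopping-rule consequence is therefore conditional, and only its direction is secure.
- Six months is the window of a composite failure event, and the plan sets no time point for reporting NRM. The figures illustrate a difference and do not reproduce a planned analysis. At a lag of 0.5 month the difference is small for at most 36 patients.
- A lower value on the transplant clock is a different quantity. It misleads if compared with a benchmark on another clock, or read as NRM in all transplanted patients. The clock behind the historical 0.45 is not stated, so bias in favour of the product is possible but not shown.

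**Conclusion.** The concern holds. The plan gives time to NRM two incompatible origins, and the choice changes the reported result. In CTL recipients analysed without delayed entry, NRM at any fixed time is no higher on the transplant clock. This follows from who is analysed and needs no assumed rate.

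The size rests on the assumed lag and constant hazards. For 0.60 at 6 months from infusion, the fall ranges from about 0.01 (lag 0.5 month, heavy relapse) to about 0.14 (lag 2 months, no relapse). A weaker stopping rule would follow only if transplant-based times entered TFU. The point should be fixed because it concerns a primary endpoint, although the better reading is already clear from the surrounding text.

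**What to change.** - In the NRM definition under Treatment and Primary Outcomes, replace the date of transplantation with the date of autologous CTL infusion as the origin of T and of the NRM analysis. Keep relapse as the competing event.
- In Treatment Failure Event and Stopping Rules, state that each patient's contribution to TFU starts at infusion.
- If NRM from transplant is also wanted, list it as a separate analysis with delayed entry (left truncation) at infusion and relapse as the competing event.
- As supporting detail, state the time origin and population behind the historical 0.45, so that the comparison is on one clock.

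The cost is one sentence, one clause and one check of the historical source. No new data are needed, since outcomes are already to be recorded from T-cell administration.
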